Document Title: Study Protocol

Protocol Title: Menopausal Sleep Fragmentation: Impact on Body Fat Gain Biomarkers in Women

Protocol #: MGB Human Research Committee #2016P002821

NCT: 03047330

Document date: January 3, 2024

**PARTNERS HUMAN RESEARCH COMMITTEE
PROTOCOL SUMMARY**

Answer all questions accurately and completely in order to provide the PHRC with the relevant information to assess the risk-benefit ratio for the study. Do not leave sections blank.

PRINCIPAL/OVERALL INVESTIGATOR

[name], MSc

PROTOCOL TITLE

Menopausal Sleep Fragmentation: Impact on Body Fat Gain Biomarkers in Women

FUNDING

National Institute of Health – National Institute on Aging

VERSION DATE

1/3/2024

SPECIFIC AIMS

Concisely state the objectives of the study and the hypothesis being tested.

Aim #1: To determine the impact of menopause-related sleep fragmentation on metabolic and behavioral biomarkers of body fat gain using an experimental sleep disruption paradigm to fragment sleep in healthy female volunteers

Hypothesis 1a: Experimental sleep fragmentation will result in an adverse adipokine profile as a metabolic biomarker for body fat gain

Hypothesis 1b: Experimental sleep fragmentation will result in increased hunger and caloric intake

Hypothesis 1c: Sleep disruption due to hot flashes will result in an adverse adipokine profile and increased hunger and caloric intake

Aim #2: To examine if hot flashes are associated with metabolic and behavioral biomarkers of body fat gain using an experimental hormone suppression paradigm in healthy women

Hypothesis 2: Hot flash frequency will correlate with a worse adipokine profile and increased hunger and caloric intake

Aim #3: To determine if estradiol withdrawal adversely affects metabolic and behavioral biomarkers of body fat gain using an experimental hormone suppression paradigm in healthy women

Hypothesis 3: Experimental withdrawal of estradiol will correlate with a worse adipokine profile and increased hunger and caloric intake

Aims 1–3 Exploratory Hypotheses:

1) Experimental sleep fragmentation mimicking menopause-related sleep disruption will reduce resting energy expenditure. 2) Baseline levels of total body fat and visceral adiposity will influence

the metabolic and behavioral response to sleep fragmentation, hot flashes, and estradiol withdrawal. 3) Negative mood state will correlate independently with an adverse adipokine profile and increased hunger and caloric intake.

BACKGROUND AND SIGNIFICANCE

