Forty women ages 18–45 years will complete a protocol involving open-label treatment with standard-dose depot leuprolide to induce hypo-E2 in all women and generate HF in approximately 2/3, thereby mimicking menopause (see **Schema**). As part of the protocol, subjects will be admitted to the BWH Clinical And Translational Science Center/Center for Clinical Investigation (CCI) inpatient unit for a total of 10 nights over a 2-month period (see **Schema**). Assessments will be divided into 2 sleep blocks. Each SB includes 2 nights during which sleep is undisturbed and 3 nights during which sleep is experimentally fragmented. Using PSG, sleep patterns will be experimentally interrupted to the same target level for all subjects during all fragmented nights using auditory procedures to mimic the menopausal hot flash-associated sleep maintenance problem. The in-lab sleep blocks will be conducted: 1) during the mid-to- late follicular phase of the menstrual

cycle when E2 is high; and 2) after at least 4 weeks on leuprolide when HF are prominent in a subset of subjects.

Participants will be given a standardized eucaloric diet for several days preceding the inpatient admission, as well as for the first four days of the inpatient visit. On one day before admission, and on the final day of inpatient admissions, subjects will have an ad lib diet. Fasting adipokine levels will be measured and leptin levels will be obtained to determine the 24-hour leptin profile under standardized eucaloric diet conditions. Food intake and macronutrient composition will be assessed as key behavioral biomarkers for body fat gain when the diet is ad lib. Hunger will be measured under both eucaloric and ad lib dietary conditions. Secondary and exploratory measures of objective HF using skin conductance monitors, negative mood/affect, reward seeking behaviors, and appetite/food preference will also be obtained. Behavioral measures will continue to be assessed at home after the 2nd SB is complete.

Protocol Schema

Study Sample and Criteria

Informed consent will be obtained from up to 130 healthy non-pregnant premenopausal women 18-45 years who do not have hot flashes in order to have 40 women complete study procedures.

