metabolic and stress markers will be collected during each visit. Blood samples will be collected repeatedly up to every 30 minutes during each visit. Blood will be drawn without interrupting sleep using an approximately 72" long IV line from outside the room and a blood-sparing technique to minimize blood loss. If issues with the IV occur, then select samples, up to 2 per wake episode may be drawn via venipuncture. Core Body Temperature will be measured with an oral thermometer. Hunger will be measured under both eucaloric and ad lib dietary conditions by administering Hunger Visual Analog Scales. On the day of admission, reproductive hormone levels will be tested, a urine pregnancy test will be performed, and morphometric measures will be gathered. During the inpatient stay, subjects will complete various questionnaires and tasks (e.g. Food Preference Questions, the Dutch Eating Behavior Scale, the Positive and Negative Affect Scale, hot flash diaries, reward seeking behavior, PSQI, ISI, PHQ-8). After waking, subjects may complete the post-sleep questionnaire and the CCI IPM Exit Questionnaire, which are regularly administered by CCI inpatient unit staff. Subjects may also complete neurobehavioral testing administered automatically by the computers on the CCI inpatient unit. Throughout the inpatient portions of the study urine voids may be scheduled to be collected approximately every 3 hours when the subject is awake. Unscheduled urine voids during the day or overnight may also be collected. For each void, the urine volume will be measured, and aliquots may be saved for later hormonal, metabolite, or electrolyte analysis of analytes that may be affected by sleep fragmentation and/or changes in hormonal status. Urine samples will be collected and stored per standard techniques. Skin conductance may be measured using the Biolog skin conductance monitor. During the 4 days prior to admission, subjects will receive several days of eucaloric meals from the CCI Nutrition Service, and ad lib breakfast will take place at BWH in order to measure food intake. Subjects will be instructed to standardize their sleep patterns during the 4 days at home, and up to a week beforehand, to extend the standardized routine.

- **Undisturbed procedures only:** Bedtime and wake-up time will be fixed to an 8-hour standardized TST.

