Document Title: Statistical Analysis Plan

Protocol Title: Menopausal Sleep Fragmentation: Impact on Body Fat Gain Biomarkers in Women

Protocol #: MGB Human Research Committee #2016P002821

NCT: 03047330

Document date: January 3, 2024

Biostatistical Analysis

Analysis approach: Metabolic endpoints are: 1) fasting morning levels of leptin (primary), adipokines, ghrelin (secondary), and 2) the circadian leptin profile (exploratory), calculated as area under curve (AUC) to detect whether the overall profile is lower, as seen in sleep restriction studies,⁵³ and morning fasting AD levels. Behavioral endpoints are: 1) satiety (primary) and hunger (secondary) on a VAS scale, and 2) daily caloric intake during ad lib meals (exploratory). Analyses of each endpoint will be conducted in parallel as we seek to detect coherence among endpoints and focus on consistency across different outcomes in each hormonal and HF context.

Our experimental design, methodology, and analytic approach are robust and unbiased. While only women will be enrolled, analyses and interpretation of results will take into consideration age and other relevant biological variables. Key covariates will be measured and included as potential predictors in multivariate analyses, including specific *a priori* examination for age, race, BMI, SES, and stressful events to reduce unexplained variability in the outcomes.¹⁴¹ Importantly, within-subject analyses using each woman as her own control and expected low attrition based on our prior experience with similar protocols will minimize potential bias.

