To address **Aim 3** (*impact of estradiol withdrawal on metabolic and behavioral biomarkers of body fat gain*), the mean levels in each endpoint in response to estradiol withdrawal (**Hypothesis 3**) will be examined using repeated-measures generalized linear mixed-model regression. Models will incorporate the 2 estrogenized and hypo-E2 contrasts addressing simultaneously the impact of estradiol withdrawal in the unfragmented and fragmented sleep states. If there is an omnibus effect of estradiol withdrawal, we will conduct post-hoc analyses on each sleep state contrast to explore whether the impact of estradiol withdrawal is consistent across both sleep states. Exploratory analysis will include adjusting for HF – either categorical (yes/no or

none/infrequent/frequent) or continuous – and sleep HF-related disruption in the hypo-E2 state (second SB).

Exploratory Hypothesis #1 analyses will involve a repeated-measures generalized linear mixed-model regression similar to those proposed for the **Hypothesis 1a** analysis using the RQ as an indirect measure of resting EE as the dependent measure, and the same post-hoc paired contrasts and interaction terms for randomization order. **Exploratory Hypothesis #2** analyses will involve addition of interaction terms (between total body fat or visceral adiposity with sleep fragmentation, HF, or E2 withdrawal) to models described for **Aims 1–3**, to test for effect modification on each metabolic or behavioral endpoint. These analyses are by necessity exploratory in nature given the sample size of this complex experimental study. **Exploratory Hypothesis #3** will involve an omnibus repeated-measures regression model encompassing all 6 contrasts described in **Aims 1–3** with the PANAS Negative Affect scale score as the primary predictor and adjustment for fragmented versus undisturbed sleep given an expected association between sleep fragmentation and affect. Post-hoc analyses using paired t-tests on each SB contrast will be conducted to explore the potential variability of the impact of negative affect on each metabolic and behavioral biomarker across the sleep fragmentation, HF, and hormonal contexts. Psychological and cognitive factors driving eating behaviors on the DEBQ will also be explored.

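### Exploratory Hypothesis 3 concerns mood state, but the SAP enters PANAS Negative Affect as one undivided predictor and does not say whether the within-woman or a mixed slope will be tested

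*SAP*

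**What the plan says.** The protocol (Specific Aims, Aims 1–3 Exploratory Hypotheses) states the hypothesis as "Negative mood state will correlate independently with an adverse adipokine profile and increased hunger and caloric intake". The SAP paragraph on Exploratory Hypothesis #3 plans "an omnibus repeated-measures regression model encompassing all 6 contrasts", "with the PANAS Negative Affect scale score as the primary predictor and adjustment for fragmented versus undisturbed sleep". It then adds: "Post-hoc analyses using paired t-tests on each SB contrast will be conducted".

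The predictor is measured repeatedly. The protocol (Detailed Description of Sleep Blocks, procedures common to both sleep conditions) lists "the Positive and Negative Affect Scale, hot flash diaries" among the inpatient questionnaires and tasks. On the blocks, the protocol Overview says: "Each SB includes 2 nights during which sleep is undisturbed and 3 nights during which sleep is experimentally fragmented". Two blocks with two sleep states each give four conditions per woman.

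Two general statements in the SAP (Analysis approach) bear on the point. One promises "within-subject analyses using each woman as her own control". The other lists covariates for examination as potential predictors: "age, race, BMI, SES, and stressful events". Neither usual affect nor a woman's mean PANAS score is in that list. Neither document mentions centring on the woman's own mean, a person-mean term, subject fixed effects or change scores for PANAS.

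**The concern.** PANAS Negative Affect can vary in two ways. Some women score higher than others on every occasion (trait), and each woman's score moves between occasions (state). The hypothesis names the state.

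The sleep and hormone contrasts of Aims 1–3 are set by design and vary within each woman, so she serves as her own control for them. PANAS is observed, not assigned, and that protection does not carry over to it automatically. With one coefficient on the undivided score and a random subject effect or a working correlation, both kinds of variation feed the estimate. Adjusting for fragmented versus undisturbed sleep removes a difference between conditions. It does not remove stable differences between women.

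At stake is the interpretation of an exploratory result. A significant coefficient could reflect which women tend towards negative affect and also have, say, higher leptin or appetite, with no association between changes in mood and changes in the outcome. It would then be reported as an independent mood-state association.

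**Working it through.** **The plan's own figure.** The SAP gives no figure for this hypothesis. Its only sample-size figure is the detectable correlation for the main study, which reproduces with the two-sided Fisher z formula r = tanh[(1.960 + 0.842)/√(n − 3)]:
- n = 40: tanh(2.802/√37) = tanh(0.461) = 0.431 (SAP: 0.43 in absolute value).
- n = 26: tanh(2.802/√23) = tanh(0.584) = 0.526 (SAP: 0.52, where power is 78.9%).

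This fixes n = 40 as the working sample but says nothing about PANAS.

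**Step 1: what the single slope estimates.** With m = 4 occasions and a random intercept, the generalised least-squares slope is

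b = (W·b_within + ψ·B·b_between) / (W + ψ·B),

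where B = 4·ICCx + (1 − ICCx), W = 3·(1 − ICCx) and ψ = (1 − ICCy)/(1 + 3·ICCy). ICCx is the between-woman share of PANAS variance and ICCy that of the outcome. The weight on the between-woman slope is ψB/(W + ψB).

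The documents give neither ICC, so both are assumptions. Two cases for PANAS:
- Equal between and within SDs: ICCx = 0.5, B = 2.5, W = 1.5.
- SDs 1.0 and 0.6: ICCx = 1/(1 + 0.36) = 0.735, B = 3.206, W = 0.794.

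| Outcome ICC | ψ | Between weight, SDs 1.0/0.6 | Between weight, equal SDs |
|---|---|---|---|
| 0.5 | 0.200 | 0.641/1.435 = 45% | 0.500/2.000 = 25% |
| 0.7 | 0.097 | 0.310/1.104 = 28% | 0.242/1.742 = 14% |
| 0.9 | 0.027 | 0.087/0.881 = 10% | 0.068/1.568 = 4% |

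With an independence working correlation (ICCy = 0 in the formula, so ψ = 1) the weight is 2.5/4.0 = 63% at ICCx = 0.5. With subject fixed effects it is zero.

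**Step 2: how often a null state effect is declared significant.** Simulation of 40 women on four occasions, true within-woman effect zero, random-intercept feasible GLS with a sleep-condition term, two-sided 5% test. The trait–outcome correlation is between a woman's usual PANAS level and her usual outcome level.

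| Trait–outcome correlation | PANAS SDs, between/within | ICCy 0.5 | ICCy 0.7 | ICCy 0.9 |
|---|---|---|---|---|
| 0.4 | 1.0/0.6 | 36% | 29% | 14% |
| 0.2 | 1.0/0.6 | 12% | 10% | 7% |
| 0.4 | equal | 20% | 15% | 8% |
| 0.2 | equal | 9% | 8% | 6% |
| 0 | either | about 5% | about 5% | about 5% |

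The within-woman slope rejected in about 4–6% throughout.

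**Step 3: check with a different fit.** A REML random-intercept model adjusted for sleep state and block, with a trait–outcome correlation of 0.43, ICCx 0.5–0.7 and ICCy 0.3–0.8, gave 11–37% for the undivided score. The deviation term, after the split, gave 4–6%, with a mean estimate of about zero.

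**Step 4: the post-hoc tests.** As described, the paired t-tests compare an outcome between two conditions and contain no PANAS term. They are within-woman, but they do not estimate a within-woman mood slope.

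**The case against.** A reader might infer that the SAP enters the raw score in a mixed model and so counts differences between women as an effect of mood. The documents do not support that as a statement of fact. The SAP refers only to the scale score and is silent on centring. It names mixed models for Aims 1–3 and Exploratory Hypothesis 1, but for this hypothesis says only repeated-measures regression. Fixed subject effects would remove the problem, and the general own-control statement is consistent with them. This objection stands: the defect is an unspecified predictor, and the slope is a mix, not a purely between-woman quantity.

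A second objection is that the hypothesis says correlate, and a between-woman correlation is not false in itself. That is fair, and is why the between-woman term should be reported and not discarded. But the hypothesis says mood state, and a between-woman association does not answer a question about state.

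Third, the larger rates depend on PANAS varying more between women than within. The protocol excludes current depression and a lifetime history of several psychiatric disorders, which could narrow trait differences, while the sleep and hormone manipulations could widen within-woman variation. This also stands: with equal SDs the rates fall by roughly 40–45% at correlation 0.4 and are close to nominal at 0.2.

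Fourth, BMI and the other listed covariates may absorb part of a trait–outcome link, and the simulations include none of them. They need not absorb all of it.

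Finally, the analysis is exploratory, and the SAP looks for consistency across outcomes. That limits the consequences, but the same trait differences could affect several outcomes alike.

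**Conclusion.** The point holds as a gap in specification with a cheap remedy. As written, and unless subject effects are fixed, the PANAS coefficient mixes trait and state associations, so it cannot by itself support a mood-state conclusion.

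The size is conditional. Over outcome ICCs from 0.9 to 0.5, a null state effect is declared significant in about 14–36% of trials (correlation 0.4) or 7–12% (0.2) with PANAS SDs of 1.0 between and 0.6 within, and in about 8–20% or 6–9% with equal SDs. All these inputs are assumptions. If the between-woman association is zero there is no inflation. For an outcome that is very stable within a woman, possibly fasting leptin, the between-woman weight is small. It is larger for noisier outcomes, possibly VAS satiety, hunger or ad lib intake.

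The documents do not support a reading in which any positive result would be an artefact, or in which the trial's main conclusions are at risk. The sample size and the primary and secondary analyses are untouched.

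**What to change.** In the SAP paragraph on Exploratory Hypothesis #3, replace the single PANAS predictor with two terms: each woman's mean Negative Affect score over her occasions, and her deviation from that mean on each occasion. State that the mood-state conclusion rests on the deviation term and that the mean term is reported as a between-woman association. If fixed subject effects were intended, saying so settles the mood-state part, although the between-woman association would then not be estimated.

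This takes one or two SAP sentences and two derived variables, with no new data. The price is precision. From the weights above, and ignoring the condition terms, the standard error grows by a factor 1/√(1 − between weight): 1/√0.553 = 1.34 at a weight of 45%, 1/√0.75 = 1.15 at 25%, and 1/√0.957 = 1.02 at 4%. The loss is greatest where the undivided slope draws most on differences between women.

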To address **Aim 1** (*impact of menopause-related sleep fragmentation on metabolic and behavioral biomarkers of body fat gain*), the mean levels in each endpoint in response to experimentally fragmented sleep (**Hypothesis 1a & 1b**) will be examined using repeated-measures generalized linear mixed-model regression. Models will incorporate the 2 SB contrasts addressing **Hypothesis 1a and 1b** to simultaneously compare the impact of sleep fragmentation in the HF-free, estrogenized environment (**SB_{SF1} vs. SB_{UD1}**), and hypo-E2 environment with stable HF levels (**SB_{SF2} vs. SB_{UD2}**); exploratory analyses will adjust for HF, either categorized (e.g., any versus none) or number of HF. If there is an omnibus effect of experimental sleep fragmentation, we will conduct post-hoc analyses on each SB contrast to explore whether the impact of experimental sleep fragmentation is consistent across hormonal and HF contexts. To address **Hypothesis 1c**, mean levels in outcomes will be contrasted **SP_{UD3} vs. SP_{UD1}** to assess the impact of sleep disruption related to HF in the environment without experimental sleep fragmentation, comparing those developing HF (expected N=26) with those who do not develop HF; analyses will adjust for initial E2 level.

Aim 2 (*impact of HF on metabolic and behavioral biomarkers of body fat gain*) will be examined using a repeated-measures generalized linear mixed-model regression analysis to determine the effect of HF on mean levels of in metabolic and behavioral biomarkers. The regression will include SB contrasts that assess the impact of HF in the presence (**SB_{SF2} vs. SB_{SF1}**) and absence (**SB_{UD2} vs. SB_{UD1}**) of experimental sleep fragmentation. If an omnibus effect of HF is observed, post-hoc analyses will be conducted on each SB contrast to explore whether the impact of HF is consistent across sleep fragmentation contexts. Additional analyses will substitute objectively measured HF or night-time only HF.

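### Exploratory Hypothesis #3: paired t-tests cannot identify how the impact of negative affect varies across contexts; secondarily, the consistency questions in Aims 1–3 name no estimate of the difference.

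*SAP*

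**What the plan says.** **Exploratory Hypothesis #3.** The Protocol (Specific Aims, third exploratory hypothesis) states: "Negative mood state will correlate independently with an adverse adipokine profile", and extends this to hunger and caloric intake. The SAP addresses it with a repeated-measures regression that has the "PANAS Negative Affect scale score as the primary predictor" and adjusts for fragmented versus undisturbed sleep. The follow-up step is: "Post-hoc analyses using paired t-tests on each SB contrast will be conducted to explore the potential variability of the impact of negative affect". The sentence goes on to name the biomarkers and the fragmentation, hot-flash (HF) and hormonal settings. No affect-by-context term is named.

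**Aims 1–3.** Each aim has a mixed model with two contrasts and a conditional follow-up:
- Aim 1: "If there is an omnibus effect of experimental sleep fragmentation, we will conduct post-hoc analyses on each SB contrast to explore whether" the effect is the same across hormonal and HF settings.
- Aim 2: "If an omnibus effect of HF is observed, post-hoc analyses will be conducted on each SB contrast", again to look at consistency, here across sleep states.
- Aim 3: "If there is an omnibus effect of estradiol withdrawal, we will conduct post-hoc analyses on each sleep state contrast", for the same purpose.

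None of the three names an estimate or interval for the difference between its two contrasts.

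**Neighbouring analyses.** Hypothesis 1c works on undisturbed sleep only, "comparing those developing HF (expected N=26) with those who do not develop HF". Exploratory Hypothesis #2 adds interaction terms "to test for effect modification on each metabolic or behavioral endpoint", but the modifier is adiposity. The interaction terms mentioned under Exploratory Hypothesis #1 concern randomization order.

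**The concern.** How the impact of affect varies is a question about slopes: does the association between PANAS and a biomarker differ between contexts? A paired t-test compares two means of one variable and contains no association. The named method therefore answers a different question, and no other analysis in the SAP answers the stated one. A reader of the results could take a significant t-test in one context and a non-significant one in another as a sign that mood matters more in the first, when only the means differ.

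The aims have a milder form of the same gap. Whether two contrasts agree is a question about their difference. Analysing each one separately leaves the reader with two results and no interval for the quantity of interest, and with nothing at all if the omnibus effect is absent.

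**Working it through.** **Inputs.** From the SAP (Sample size and Hypothesis 1c): 40 completers, of whom 26 are expected to develop HF, leaving 40 − 26 = 14; alpha 0.05; 80% power; detectable correlation 0.43 in absolute value. The SAP's figure reproduces two-sided by Fisher z: tanh((1.960 + 0.842)/√37) = tanh(0.461) = 0.43. That correlation concerns EEG arousals and leptin. It is borrowed here as a plausible affect slope. The documents give no SD for any contrast and no correlation (rho) between contrasts, so contrast SD = 1 and rho = 0 to 0.5 are assumptions.

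**1. What one paired t-test responds to** (simulation, n = 40, biomarker measured in two conditions):

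| Affect slope in the two conditions | Mean affect shift | Direct biomarker shift | Paired t-test rejects | Slope-difference test rejects |
|---|---|---|---|---|
| 0 and 0.8 | 0 | 0 | 5.0% | 97.7% |
| 0.6 and 0.6 | 0.5 | 0 | 35.9% | 4.9% |
| 0 and 0 | 0 | 0.45 | 80.4% | 4.8% |

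In the first row the slopes differ and the t-test stays at its null rate. In the other two the slopes are equal and it rejects because the mean moved.

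**2. Comparing t-tests across two contexts** (n = 40, mean change 0.45 SD when the slope is 0.43). Disagreement means that exactly one of the two tests is significant.

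*Affect does not shift on average.* Both contrasts have mean 0.45 SD whatever the slope, and each test has power 0.793. At rho 0 the disagreement is 2 × 0.793 × 0.207 = 0.33, for slopes 0.43/0.43 and for 0.43/0 alike.

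*Affect shifts by 0.5 SD in each contrast, direct effect 0.235 SD.* With slope 0.43 the mean is 0.235 + 0.43 × 0.5 = 0.45 SD (power 0.793). With slope 0 it is 0.235 SD (power 0.305). At rho 0:
- Slopes 0.43/0.43: 0.33.
- Slopes 0.43/0: 0.793 × 0.695 + 0.207 × 0.305 = 0.551 + 0.063 = 0.61.

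At rho 0.5, simulation gives 26% and 53%.

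*Why this is confounding.* Keep the slope at 0.43 in both contexts, but let affect shift by 0.5 SD in the first and by nothing in the second. The means are again 0.45 and 0.235 SD, and the disagreement is again 61% at rho 0. The t-tests cannot tell a different slope from a different mood shift.

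**3. What the affect-by-context terms would deliver.** Over residual and affect correlations of 0 to 0.5, with no mean affect shift, a slope-difference test rejects in 5–6% of trials when the slopes are equal, 48–69% for 0.43 against 0, and 18–27% for 0.43 against 0.2. For PANAS-by-HF (26 against 14 women), power is 25% for 0.43 against 0 and 11% for 0.43 against 0.2, with a CI half-width of about 0.68 SD per SD.

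**4. The difference of contrasts in Aims 1 and 3.** With SF for fragmented sleep, UD for undisturbed sleep and the number for the block, (SF2 − UD2) − (SF1 − UD1) = (SF2 − SF1) − (UD2 − UD1). One quantity therefore serves Aim 1, and also Aim 3 if its unlabelled contrasts mean block 2 against block 1 within each sleep state. The CI half-width is t(0.975, 39) × √(2(1 − rho)/40): 2.023 × 0.2236 = 0.45 SD at rho 0, and 2.023 × 0.1581 = 0.32 SD at rho 0.5. Power to separate 0.45 from 0.15 SD is 26–46%.

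**5. Why that quantity does not serve Aim 2.** In block 2 all 40 women are meant to be estrogen-suppressed, but only 26 are expected to have HF. The all-women contrast therefore mixes HF with estradiol withdrawal and includes about 14 women without HF.

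**The case against.** **The t-tests may still carry some signal.** The SAP itself expects affect to be associated with sleep fragmentation. If affect shifts and passes through to the biomarker, the pattern of t-tests does change with the slope (33% against 61% above). This stands. A reader might infer that the t-tests carry no information on the slope, but that holds only if affect does not shift on average. What the SAP supports is narrower: slope and mean shift are confounded, so the slope difference cannot be identified.

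**The hypothesis is still tested.** A reader might infer that Exploratory Hypothesis #3 has no valid analysis. The main regression has PANAS as its predictor and addresses the Protocol's hypothesis. Only the follow-up fails.

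**The aims are not analysed wrongly.** Aim 1 fits both contrasts in one model so as to compare them together, and the difference is a linear combination already available from it. Follow-up after an omnibus effect is ordinary practice. Both points stand, so this part concerns incomplete reporting. A reader might also infer that consistency will be judged by whether both contrasts are significant. With equal true effects of 0.45 SD, exactly one would then be significant in 23–33% of trials. The SAP states no such rule, so that rate does not describe this plan.

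**Power is low.** It is, and the intervals will be wide. That is a reason to report intervals and claim little; it does not make a test of a different quantity suitable.

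**Conclusion.** The point holds and is minor. The paired t-tests under Exploratory Hypothesis #3 cannot answer the question they are assigned, because they contain no affect term and respond to mean shifts. This follows from what a paired t-test is and needs no assumed value. The percentages illustrate it and rest on a borrowed slope of 0.43, unit contrast SD, an assumed affect shift of 0 or 0.5 SD and rho of 0 to 0.5.

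The missing estimate of the difference between contrasts in Aims 1 and 3 is a secondary reporting improvement, as is the missing HF-by-fragmentation estimate in Aim 2. The main PANAS regression, the main tests of the aims and the sample size are not affected.

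**What to change.** **Exploratory Hypothesis #3.** Replace the paired t-tests with PANAS-by-fragmentation, PANAS-by-block and PANAS-by-HF terms (with the matching main effects) in the planned mixed model. Report them as exploratory estimates with 95% CIs. State that power for slope differences is low, above all for PANAS-by-HF, which rests on an expected 26 against 14 women in block 2.

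**Aims 1 and 3.** For each endpoint, report (SF2 − UD2) − (SF1 − UD1) from the planned model with a 95% CI, whatever the omnibus result. Label it exploratory, and state that a non-significant difference is not evidence of consistency. Say whether the Aim 3 contrasts are block 2 against block 1 within each sleep state; the use of this quantity for Aim 3 depends on that reading.

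**Aim 2.** Use an HF-by-fragmentation term in block 2, also exploratory. It compares women with and without HF, so it is less precise than a purely within-woman contrast.

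**Cost.** SAP wording, a few interaction terms, and one contrast per endpoint in a model already planned. No new data or visits. The downside is a few extra exploratory estimates with wide intervals.
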